11.1.1 Datasets to be Analyzed, Analysis Populations

Data will be analyzed as intention to treat after all participants have finished the study.

11.1.2 Primary Analysis

Analysis will be done by the investigators. For our primary analysis, we will compare the two arms with a Fisher's exact test and we will also estimate effect size with a logistic regression model reporting odds ratios (OR) and corresponding 95% confidence intervals using STATA. All tests will be two tailed; $p < 0.05$ will be defined as significant.

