Outcome(s):	
Primary: The primary endpoint of this study is achievement of metabolic control without anti-diabetic medication 3 months after study enrollment. For the purpose of this study, metabolic control is defined as an HbA1c below a target stratified for three groups according to HbA1c at baseline: HbA1c >14% → target < 10%; HbA1c < 14% and > 10% → target < 8%; HbA1c < 10% → target < 7.5%
 
Secondary:
 
 - Absolute HbA1c reduction per stratification group (groups consist of HbA1c > 14 %, HbA1c < 14 % and > 10 % and HbA1c < 10 %) - Change of HbA1c at 6 and 12 months after enrollment compared to control group - Proportion of patients achieving target per stratified group after 3 and 6 months without anti-diabetic medication other than Metformin - Changes in pH, base excess and bicarbonate 90 minutes after bicycle exercise compared to baseline - Change of weight at 3, 6 and 12 months after enrollment compared to baseline and to standard of care - Changes in blood glucose at the end of, as well as 30 and 90 minutes after bicycle exercise compared to baseline - Feasibility of bicycle exercise at study enrollment in the ER, defined as absence of problem reports through the study team (e.g. patient cooperation) - Safety of bicycle exercise, defined as: 
 o Absence of SAEs during the exercise o No signs of acute cardiopulmonary decompensation in patients during bicycle exercise o No necessity to prematurely terminate the bicycle intervention because of other health or safety concerns - Safety of intensive lifestyle intervention within 3 months following study enrollment, with the following endpoints: 
 o Number of SAEs in the intervention group compared to the control group o Number of rescue medication administered in the intervention group compared to the control group - Length of initial hospitalization, as well as number and length of re-hospitalizations and unplanned re-consultations within 3 months after initial consultation - Changes in physical activity at 6 months compared to baseline assessed by SIMPAQ questionnaire (Endpoint: hours of physical activity) - Changes in physical activity at 3 and 6 months compared to baseline assessed by actigraph (Endpoint: Stepgoal reached) - Number of anti-diabetic medication at 30, 60, 90 days, as well as 6 months and one year compared to baseline in both arms - Proportion of patients receiving insulin therapy after 6 months and one year in the intervention group compared to the control group - Absolute health-care related costs at 3, 6 and 12 months in both arms - Quality of life at 6 months in the intervention group compared to standard of care as assessed by SF-36 questionnaire.

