Study Duration:	The primary endpoint will be assessed at 3 months. The overall study duration is 1 year.
Study Schedule:	11/2018 of First-Participant-In (planned) 12/2025 of Last-Participant-Out (planned)
Investigator(s):	Investigators: [name], [name]-PhD, and [name] Division of Endocrinology, Diabetes and Metabolism Department of Internal Medicine University Hospital Basel, Switzerland [contact] [contact] [contact] [contact]
Study Centers:	Department of Medicine, University Hospital Basel Department of Medicine, Cantonal Hospital Olten Hôpital du Jura - site de Delémont
Statistical Considerations:	All subjects will be considered on a per-protocol basis. For our primary analysis, we will compare the two arms with a Fisher's exact test and we will also estimate effect size with a logistic regression model reporting odds ratios (OR) and corresponding 95% confidence intervals. All tests will be two-tailed; p<0.05 will be defined as significant. Data will be analyzed using Graph Pad Prism, STATA and IBM SPSS.
GCP Statement:	This study will be conducted in compliance with the protocol, the current version of the Declaration of Helsinki, the ICH-GCP or ISO EN 14155 (as far as applicable) as well as all national legal and regulatory requirements.

ABBREVIATIONS

ADA	American Diabetes Association
AE	Adverse event
ASR	Annual safety report
BASEC	Business Administration System for Ethical Committees, (https://submissions.swissethics.ch/en/)
BGA	Blood gas analysis
CA	Competent authority (e.g. Swissmedic)
CEC	Competent ethics committee
ClinO	Ordinance on Clinical Trials in Human Research (in German: KlinV, in French: OClin, in Italian: OSRUM)
CRF	Case report form
CTCAE	Common terminology criteria for adverse events
CTU	Clinical Trial Unit
DSBG	Departement für Sport, Bewegung und Gesundheit
EC	Ethics committee
ECG	Electrocardiogram
eCRF	Electronic case report form
EKNZ	Ethikkommission Nordwest- und Zentralschweiz
ER	Emergency room
GCP	Good clinical practice
H_0	Null hypothesis
H_1	Alternative hypothesis
HbA1c	Glycated hemoglobin A
ICF	Informed consent form
ICH	International Council for Harmonisation of Technical Requirements for Pharmaceuticals for Human Use
ISF	Investigator site file
ISO	International Organisation for Standardisation
MHR	Maximum heart rate
SAE	Serious adverse event
s.c.	Subcutaneous
SIMPAQ	Simple physical activity questionnaire
SIRS	Systemic inflammatory response syndrome
SNCTP	Swiss National Clinical Trials Portal

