5. STUDY OUTCOMES

5.1 Primary Outcome

The primary endpoint of this study is achievement of metabolic control with intensive lifestyle intervention 3 months after study enrollment. For the purpose of this study, metabolic control is defined as a fasting glucose < 7.6 mmol/l and an HbA1c below a target stratified for three groups according to HbA1c at baseline: HbA1c > 14 % → target < 10 %; HbA1c < 14 % and > 10 % → target < 8 %; HbA1c < 10 % → target < 7.5 %.

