6.1.2 Blinding Procedures

Blinding of patients and study personal is not possible for this study.

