9.1.1 Assessment of Primary Outcome

Glycated hemoglobin A1c will be measured by the same means (POCT or venous blood sampling) as done at baseline, and 3 months after enrollment.

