12.1.6 Analysis and Archiving

The EDC system will be locked after all data is monitored and all raised queries have been resolved.

Data is exported and transferred to the investigator by the CTU Basel according to internally defined

processes. The exported data will be archived by the investigator.

Data for analysis will be extracted from the database export and analysis will be conducted with Graph Pad Prism. Source data/documents and p-CRFs will be stored at study site for at least 10 years and be destroyed thereafter.

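### The primary analysis goes to unblinded investigators on a data export with no step withholding the arm, so choices the protocol leaves open can be made with arm and result in view

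*Protocol*

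**What the plan says.** **Who analyses.** Section 11.1.2: "Analysis will be done by the investigators". Section 6.1.2: "Blinding of patients and study personal is not possible for this study". Section 12.1.6: "Data is exported and transferred to the investigator by the CTU Basel". No section shown describes withholding or recoding the arm before the responder status or the analysis set is fixed.

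**What is analysed.** The protocol is not of one mind.
- The Study Synopsis gives the endpoint as "achievement of metabolic control without anti-diabetic medication 3 months after study enrollment" and then defines control by HbA1c targets alone.
- Section 5.1 adds a glucose criterion: "metabolic control is defined as a fasting glucose < 7.6 mmol/l and an HbA1c below a target stratified for three groups". It puts no drug-free condition into the definition. Section 11 (Hypothesis) repeats the 5.1 definition, while the sample-size paragraph speaks of success with no anti-diabetic drugs.
- The HbA1c strata use strict inequalities on both sides: "HbA1c < 14 % and > 10 % → target < 8 %; HbA1c < 10 % → target < 7.5" %.
- On the analysis set, the synopsis says "All subjects will be considered on a per-protocol basis", whereas section 11.1.1 says intention to treat.

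**How it is measured.** Section 9.1.1: "Glycated hemoglobin A1c will be measured by the same means (POCT or venous blood sampling) as done at baseline", and again at 3 months.

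**The concern.** Care cannot be blinded in this trial, but the step from locked data to responder status can be shielded from knowledge of the arm. The protocol provides no such step and names the investigators as analysts. That would matter little if the endpoint were one fully specified laboratory threshold, but it is not. Someone must choose between two endpoint definitions and two analysis sets, and must place patients who sit on a stratum edge.

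Some of these choices act differently in the two arms. Under section 8.1.4 controls usually receive oral drugs or insulin, so a drug-free condition bears mostly on them. Non-compliance is defined in section 7 by completion of the training programme, which only the intervention arm follows, so a per-protocol exclusion on that ground can occur in one arm only. If these points are settled after the results can be seen by arm, the reported p-value no longer has its stated error rate, and a reader cannot tell whether the choice was independent of the result.

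**Working it through.** **1. The planned size.** Inputs from section 11: 80 % v 40 %, two-sided alpha 0.05, power 80 %, 1:1 allocation, Fisher's exact test.
- Uncorrected n per arm = [1.96·√(2·0.6·0.4) + 0.842·√(0.8·0.2 + 0.4·0.6)]² / 0.4² = (1.358 + 0.532)² / 0.16 ≈ 22.3, so 23.
- With continuity correction: (22.3/4)·[1 + √(1 + 4/(22.3·0.4))]² ≈ 27.1, so 28, as stated.
- 56 × 1.10 = 61.6, so 62, as stated.
- Exact Fisher power at 28 per arm is 82.3 %.

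The sample size is therefore not in question, and masking would not change it.

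**2. Where discretion exists.**

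| Input to success status | Fixed by the protocol? |
|---|---|
| HbA1c value, baseline and month 3 | Yes: measured number, same means both times (9.1.1) |
| Visit window, day 90 ± 14 | Yes (study schedule) |
| Glucose criterion | No: in 5.1 and 11, absent from the synopsis |
| Drug-free condition | No: in the synopsis, absent from the 5.1 definition |
| Target at baseline of exactly 10 % or 14 % | No: such a patient is in no stratum |
| Analysis set | No: per protocol (synopsis) v intention to treat (11.1.1) |

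The drug-free condition is harder to apply because Table 1 allows an optional Metformin start at visit 6, the visit at which the endpoint HbA1c is taken.

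**3. What one patient can do.** Two-sided Fisher p-values at 28 per arm (intervention v control successes):

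| Successes | p | One more in the intervention arm | p |
|---|---|---|---|
| 18 v 10 | 0.060 | 19 v 10 | 0.031 |
| 20 v 12 | 0.058 | 21 v 12 | 0.029 |
| 19 v 11 | 0.060 | 20 v 11 | 0.031 |

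**4. How often that happens.** The probability that one added intervention success changes the verdict is the sum, over all pairs (x, y), of Bin(x; 28, p1)·Bin(y; 28, p2) for those pairs where significance at (x, y) differs from significance at (x + 1, y).
- 80 % v 40 %: about 7 %.
- Equal rates of 40 %, 50 % or 60 %: about 2 %.

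At the planned rates the expected counts are about 22 v 11 (0.8 × 28 = 22.4; 0.4 × 28 = 11.2), p = 0.006. Three intervention successes must be lost, down to 19 v 11 (p = 0.060), before significance goes.

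**5. Type I error if intervention failures are counted as successes.** Assumed scenario: equal true rates of 40 %, 50 % or 60 %, with k intervention failures counted as successes.

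| k | Type I error |
|---|---|
| 0 | 0.023–0.026 |
| 1 | 0.029–0.034 |
| 2 | 0.044–0.057 |
| 3 | 0.072–0.098 |

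Fisher's test is conservative here. One such reclassification stays below 0.05, two reach about 0.05, and three exceed it. The documents do not allow an estimate of how many patients each open choice would move. A change of definition or analysis set could move several at once; a stratum edge would rarely move more than one.

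**The case against.** The strongest reply is that the endpoint rests on measured values against numeric cut-offs, and knowledge of the arm cannot turn a recorded 7.6 % into a value below 7.5 %. The database is locked after monitoring and query resolution, before export (12.1.6), and an audit trail records every change with reason, time and user (12.1.7). This stands: it rules out a general claim that borderline laboratory classifications are open to influence.

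A reader might infer that the treating physicians themselves derive the endpoint. The text does not say so. It names the investigators as analysts, but not who derives responder status, nor that the analysts are those who treat. The contents page lists a statistician, but that section is not available, so the statistician's role cannot be judged.

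It can also be said that the contradictions are the root cause, and that reconciling them removes most of the discretion with or without masking. That is largely right, and the fix begins there.

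Masking is also imperfect. Month-3 medication reveals the arm for many patients, since controls usually receive drugs (8.1.4) and the intervention arm has none before month 3 except as rescue (8.1.1; section 8, Concomitant Interventions). Masked derivation is therefore cheap rather than free, and only partial.

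Finally, such procedures are often left to a statistical analysis plan. That does not dispose of the point, because the protocol itself assigns the analysis to unblinded people and itself states the conflicting definitions.

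**Conclusion.** The point holds as a low-cost improvement. The protocol places the primary analysis with investigators in an unblinded trial, provides no step that withholds the arm, and leaves four choices open that determine success or inclusion. Those choices can therefore be made with arm and result in view. Nothing in the documents shows that they would be.

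A reader might go on to infer that one reclassified patient of 56 decides the trial. That is true only next to the threshold: about 7 % of trials at 80 % v 40 %, and about 2 % under equal rates. These figures assume 28 evaluable patients per arm, independent binomial outcomes, the two-sided Fisher test, and a single change in favour of the intervention arm. Type I error exceeds 0.05 throughout the 40–60 % range only when three intervention failures are counted as successes. The exposure is greater if the definition or the analysis set is chosen late, because that can move several patients, and unevenly between arms. Its size cannot be computed from the documents.

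**What to change.** In sections 5.1, 11 and the synopsis, before any unblinded look:
1. State one endpoint definition. The sponsor must reconcile whether the glucose criterion and the drug-free condition belong to it, and how a Metformin start at visit 6 or earlier rescue medication counts.
2. Close the strata edges so that baselines of exactly 10 % and 14 % each belong to one stratum.
3. Name one primary analysis set: intention to treat, as in 11.1.1.

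In sections 11.1.2 and 12.1.6, add:

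4. After database lock the CTU first exports, without the arm, baseline and month-3 HbA1c, month-3 fasting glucose, visit dates, and month-3 anti-diabetic medication as a yes/no flag derived by a fixed rule.
5. The responder-derivation code and the analysis-set list are written and frozen on this file.
6. Only then does the CTU release the arm and the visit 2–5 data, which exist only for the intervention arm, and the Fisher test is run.

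**Cost.** A few sentences, one extra export by the unit that already exports the data, and a short delay; no extra patients. **Limits.** Masking is incomplete because medication status partly reveals the arm, and the step does nothing about bias from unblinded treatment decisions during the trial. Freezing rules and code before the arm is released is the part that protects the result; hiding the arm supports it.

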11. STATISTICAL METHODS

Hypothesis

We hypothesize that lifestyle intervention lowers HbA1c effectively without antidiabetic drugs. The null-hypothesis (H_0) is that there will be no significant difference between the proportions of patients achieving metabolic control in the intervention group and the control group. The alternative hypothesis (H_1) is that there will be significantly more patients achieving metabolic control in the intervention group. For the purpose of this study, metabolic control is defined as a fasting glucose < 7.6 mmol/l and an HbA1c below a target stratified for three groups according to HbA1c at baseline: HbA1c $> 14\% \rightarrow$ target $< 10\%$; HbA1c $< 14\%$ and $> 10\% \rightarrow$ target $< 8\%$; HbA1c $< 10\% \rightarrow$ target $< 7.5\%$.

Determination of Sample Size

The aim of this study is to assess whether bicycle exercise followed by an intensive life style intervention can sufficiently restore metabolic control without anti-diabetic drugs as compared to a standard care control group.

Based on our clinical experience we assume that 80 % in the intervention group will reach the primary endpoint of metabolic control with no anti-diabetic drugs compared to only 40 % in the standard care control group.

A publication by Martinus et al.²¹ on adherence to a study sport program for newly diagnosed type 2 diabetes mellitus patients, shows up to 80 % adherence for the group that was additionally supported by a psychologist for increased motivation. The adherence to the program was significantly better in the group with support by the psychologist, as were the results regarding improvement of physiological parameters such as body mass, fat mass or strength.

A review on the effect of physical exercise on glycemic control found an average decrease of HbA1c by 0.6 mmol/l through exercise²² in diabetes patients at least one year after diagnosis and with a moderate hemoglobin elevation. Based on this data, our target ranges were extrapolated for patients with new-onset diabetes and higher HbA1c.

The inclusion of 28 patients per group (n total 62 patients including 10 % lost to follow-up) will provide 80 % power at an alpha level of 0.05. A number of 15 to 25 patients per center is envisaged.

Statistical Criteria of Termination of Trial

There will be no statistical criteria to terminate the trial early.

Planned Analyses

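### A cheap improvement, not an error: Boschloo's unconditional exact test would give more power than the planned Fisher test from the same patients, with type I error still held at 5%

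*Protocol*

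**What the plan says.** Section 11.1.2 fixes the primary comparison: "we will compare the two arms with a Fisher's exact test". The same sentence adds an effect estimate: "we will also estimate effect size with a logistic regression model reporting odds ratios (OR) and corresponding 95% confidence intervals". It continues: "All tests will be two tailed", with significance at p below 0.05. The synopsis (Statistical Considerations) repeats this. The type of interval (Wald, profile likelihood or exact) and any covariates are not named.

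Section 11, Determination of Sample Size, gives the design assumptions: "we assume that 80 % in the intervention group will reach the primary endpoint", "compared to only 40 % in the standard care control group". It states that 28 patients per group, 62 in total with 10% loss, "will provide 80 % power at an alpha level of 0.05". Section 6.1.1 describes 1:1 allocation by computer-generated random number and mentions no blocks.

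**The concern.** Fisher's test conditions on the total number of successes. With about 28 patients per arm the attainable p-values are coarse, so the test usually runs well below its nominal 5%. A logistic odds-ratio interval of the usual kind runs close to 5%. Two things follow. Some power goes unused that another exact test could recover from the same patients. And the report may show a non-significant p-value beside an odds-ratio interval that excludes 1.

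That second case is most likely when the true effect is smaller than planned. The planned effect rests on clinical experience (section 11), the trial is open-label (section 6.1.2), and the investigators run the analysis (section 11.1.2). A near miss is therefore best settled by a rule written in advance.

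**Working it through.** **Inputs.** 80% v 40%, two-sided 0.05, 80% power, 28 evaluable per arm, 62 enrolled (section 11). The 70% v 40% scenario, the Wald interval and an unadjusted logistic model are assumptions.

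**1. The plan's own figure.** Uncorrected formula, with mean rate 0.6:

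n = [1.96·√(2·0.6·0.4) + 0.842·√(0.8·0.2 + 0.4·0.6)]² / 0.4² = (1.358 + 0.532)² / 0.16 = 22.3, so 23.

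With continuity correction: n′ = (n/4)·[1 + √(1 + 4/(0.4·n))]² = 5.58 × 2.203² = 27.1, so **28**. This reproduces the protocol, and it is the version suited to Fisher's test. For losses, 56 × 1.10 = 61.6, so 62.

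**2. Size and power by full enumeration.** For arms of n1 and n2, sum Bin(a; n1, p1) × Bin(b; n2, p2) over all tables the test rejects. Size is the maximum over a common rate p1 = p2. Boschloo's test ranks tables by Fisher p-value and rejects up to the largest cut-off that keeps this maximum at or below 0.05. At 28/28 that cut-off is 0.0797.

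| Arms (intervention/control) | Fisher max size | Boschloo max size | Power 80 v 40: Fisher → Boschloo | Power 70 v 40: Fisher → Boschloo |
|---|---|---|---|---|
| 28/28 | 2.8% | 4.6% | 82.3 → 87.3% | 50.8 → 60.7% |
| 28/27 | 3.8% | 4.7% | 85.1 → 87.9% | 55.1 → 59.5% |
| 27/29 | 3.6% | 4.9% | 86.0 → 88.8% | 57.2 → 62.1% |
| 31/31 | 3.0% | 4.8% | 87.0 → 91.3% | 59.1 → 66.0% |
| 30/32 | 4.0% | 4.9% | 90.4 → 91.1% | 64.9 → 65.2% |

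The sweep covered every total from 54 to 62, with the intervention arm up to four patients from half the total (81 splits). Fisher's maximum size ran from 2.5% (29/29) to 4.2% (29/33). Boschloo's never exceeded 5.0%, and it rejected every table that Fisher rejects. The gain at 80% v 40% ran from 0.3 points (27/35) to 5.9 points (29/29), and was at least 1 point in 72 of the 81 splits. At 70% v 40% it ran from 0.2 to 10.6 points.

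**3. Test against interval.** At 28/28, 30 tables have Fisher p ≥ 0.05 with a Wald 95% interval that excludes 1. For example, 21/28 v 13/28 gives:

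- odds ratio (21 × 15)/(7 × 13) = 3.46
- SE of its log = √(1/21 + 1/7 + 1/13 + 1/15) = 0.578
- Wald interval exp(1.242 ± 1.96 × 0.578) = 1.12 to 10.7
- Fisher p = 0.054; Boschloo p = 0.031
- exact conditional interval 0.98 to 12.7, which agrees with Fisher

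Disagreement in either direction at 28/28 has probability 5.2% at 80% v 40% and 9.9% at 70% v 40%. Over the 81 splits, 74 fall between about 1 and 6% at 80% v 40% (extremes 0.2 and 6.9%), and 76 between 2 and 11% at 70% v 40% (lowest 0.3%). A likelihood-ratio interval does not remove it: 6.0% at 28/28 under 80% v 40%.

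**The case against.** The case for leaving the plan alone is strong on several counts, and most of it stands.

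- **Fisher is valid and conventional at this size.** Conservatism is not an error, and choosing another test is a preference. This stands, so the point is offered only as an improvement.
- **The planned power is delivered.** A reader might infer that the sample-size statement is wrong because Fisher runs below 5%. It is not: 28 is the continuity-corrected figure, and the exact power is 82.3%.
- **2.8% is not a general ceiling.** A reader might take it as a property of the trial. It belongs to an exact 28/28 split, which has a chance of about 11% if 56 patients are allocated by simple randomization. At 30/32 the gain in power at 80% v 40% is only 0.7 points.
- **The decision rule is readable.** Section 11.1.2 makes Fisher the comparison and the logistic model the effect estimate. Interval type and a sentence on which result governs are details that a statistical analysis plan may hold, so their absence here is no fault.
- **Non-estimable odds ratios.** A reader might argue that control successes will be rare and the odds ratio often infinite: with a 5% control rate, no success among 28 has probability 0.95^28 = 24%. That rate is not in the sample-size section, which assumes 40%. Under 80% v 40%, an arm with no success or all successes has probability 0.2%.
- **Other intervals do not fully cure disagreement.** With unequal arms, the exact conditional interval disagrees with Fisher more often than Wald does at 27/29 (2.9% v 1.8% at 80% v 40%). Boschloo with a Miettinen-Nurminen interval still disagrees at 28/27 (1.3% at 80% v 40%, 5.4% at 70% v 40%).

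What this leaves untouched is that Boschloo's test never did worse than Fisher in any split checked.

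**Conclusion.** The primary analysis is sound as written, and the stated power is met. The choice of test can still be improved at almost no cost. Moving to Boschloo's test gains about 1 to 6 points of power at the design effect and about 0 to 11 points if the intervention rate is 70%, with type I error at or below 5%. Equal or nearly balanced arms with low Fisher size gain most; some unequal splits gain almost nothing.

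The mismatch between test and interval is a secondary reporting matter, about 1 to 6% of trials at the design effect, and depends on the assumption that the interval is Wald. All figures assume an unadjusted comparison and 54 to 62 evaluable patients.

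**What to change.** Before any analysis by arm, amend section 11.1.2 and the matching synopsis entry to say:

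1. The primary test is Boschloo's unconditional exact test, two-sided at 0.05, and it alone decides significance.
2. The effect estimate is the risk difference with a score (Miettinen-Nurminen) or test-inverted 95% interval.
3. The odds ratio is secondary, with a Firth or exact interval if a cell is zero.
4. Fisher's p-value is reported as a sensitivity result.

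The sample size need not change. The cost is a few sentences, the justification and ethics committee report that section 11.1.6 requires for a change to the statistical plan, and a call to R or Python beside STATA, GraphPad Prism and SPSS. A small chance of disagreement between test and interval remains when the arms are unequal; item 1 settles how it is read.
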